5.6 Monitoring

Common vital signs (*e.g.*, blood pressure, heart rate) are to be assessed before commencement of infusion of FLOX or nivolumab. For the former, the patient will receive premedication (typically ondansetron and dexamethasone) according to each participating department's SOP.

The risks related to nivolumab therapy must be thoroughly discussed with patients randomized to the experimental arm. These subjects will also be provided with a Patient Information Card upon starting treatment. They will further receive a prescription of prednisone in case of irAE, and be informed to contact Clinical Investigator swiftly in case of suspected irAE.

5.7 Schedule modifications

5.7.1 IMP (investigational medicinal products) schedule

Continuation of IMP treatment with suspected progression is permitted; *c.f.*, [Paragraph 5.7.2.4](#). Discontinuation from study treatment may result from any of the criteria listed in [Paragraph 5.7.2.3](#).

If required, subjects may receive IMP up to 3 days before or after the scheduled date. A cycle started more than 3 days after the intended dose date will be considered a delay. Subsequent dosing should be based on the actual date of administration of the previous drug cycle.

Subjects will be monitored for infusion reactions during IMP administration. If an acute reaction is noted, subjects will be managed according to [Paragraph 5.7.2.7](#). IMP doses may be interrupted, delayed, or discontinued as per requirement.

5.7.2 Dose modifications for IMP

Dose modification is only allowed in case of dose-limiting toxicity; *c.f.*, [Appendices 5 and 6](#) for general guidelines for practical management.

5.7.2.1 Dose delay criteria for IMP

Dose delay criteria apply for all drug-related AE. A treatment delay up to 4 weeks, *i.e.*, ≤6 weeks calculated from start of the previous therapy cycle, is allowed. A treatment delay beyond 6 weeks is not allowed ([Paragraph 5.7.2.3](#)).

Tumor assessments should continue as per protocol schedule, even if dosing is delayed.

Nivolumab administration will be delayed for the following reasons (in CTCAE grading):

- Any grade ≥2 non-skin drug-related AE, except for fatigue and laboratory abnormalities.
- Any grade 3 skin drug-related AE.
- Any grade 3 drug-related laboratory abnormality.
- Any AE, laboratory abnormality, intercurrent illness, or other reason which, in the judgment of Clinical Investigator, warrants delaying the dose of study medication.

Subjects who require delay of nivolumab will be re-evaluated weekly, or more frequently if clinically indicated. Nivolumab dosing can be resumed on the established dosing schedule when retreatment criteria are met ([Paragraph 5.7.2.2](#)).

FLOX administration will be delayed for the following reasons (in CTCAE grading):

- Grade 2 diarrhea (increase of 4–6 stools per day over baseline; moderate increase in stoma output compared to baseline; not interfering with ADL).
- Grade 3 diarrhea (increase of 7 or more stools per day over baseline; incontinence; severe increase in stoma output compared to baseline; interfering with ADL).
- Grade 2 myelosuppression (neutrophils of $1.0 \times 10^9/L$ to less than $1.5 \times 10^9/L$, or platelets of $50 \times 10^9/L$ to less than $75 \times 10^9/L$).
- Grade 3 myelosuppression (neutrophils of $0.5 \times 10^9/L$ to less than $1.0 \times 10^9/L$, or platelets of $25 \times 10^9/L$ to less than $50 \times 10^9/L$).
- Grade 4 myelosuppression (neutrophils less than $0.5 \times 10^9/L$, or platelets less than $25 \times 10^9/L$).
- Grade 2 sensory neuropathy (sensory alteration or paresthesia persisting between two oxaliplatin doses with no or only minor improvement, moderate symptoms, limiting instrumental ADL).

Subjects who require delay of FLOX will be re-evaluated weekly, or more frequently if clinically indicated. FLOX administration will be resumed when retreatment criteria are met ([Paragraph 5.7.2.2](#)).

5.7.2.2 Criteria to resume dosing for IMP

Subjects may resume treatment with study drug when the drug-related AE resolves to CTCAE grade ≤ 1 or baseline value, with the following exceptions:

For nivolumab:

- Subjects may resume nivolumab treatment in accordance with the below criteria irrespective of whether FLOX or nivolumab was administered in the preceding cycle.
- Subjects may resume treatment in the presence of CTCAE grade 2 fatigue.
- Drug-related pulmonary toxicity, diarrhea, or colitis must have resolved to baseline before treatment is resumed.
- Subjects with drug-related endocrinopathies adequately controlled with only physiologic hormone replacement may resume treatment.
- Subjects who received systemic corticosteroids for management of any drug-related toxicity must be off corticosteroids or have tapered down to an equivalent dose of prednisolone ≤ 10 mg/day.

For FLOX:

- Subjects may resume FLOX treatment in accordance with the below criteria (in CTCAE grading) irrespective of whether FLOX or nivolumab was administered in the preceding cycle.
- Grade 2 diarrhea; the following pertaining to both oxaliplatin and fluorouracil: interrupt until grade 1 or less, then 100% dose first time, 75% dose second time, 50% dose third time.
- Grade 3 diarrhea; the following pertaining to both oxaliplatin and fluorouracil: interrupt until grade 1 or less, then 75% dose first time, 50% dose second time, discontinue third time.
- Grade 2 myelosuppression; the following pertaining to both oxaliplatin and fluorouracil: interrupt until grade 1, then 100% dose first time, 75% dose and consider support with granulocyte-colony stimulating factor (e.g., pegfilgrastim) second or subsequent times.
- Grade 3 myelosuppression; the following pertaining to both oxaliplatin and fluorouracil: interrupt until grade 1 or less, then 75% dose and consider support with granulocyte-colony stimulating factor (e.g., pegfilgrastim) first or subsequent times.
- Grade 4 myelosuppression; the following pertaining to both oxaliplatin and fluorouracil: interrupt until grade 1 or less, then 50% dose and consider support with granulocyte-colony stimulating factor (e.g., pegfilgrastim) first or subsequent times.
- Grade 2 sensory neuropathy; the following pertaining only to oxaliplatin: interrupt until grade 1 or less, then 75% dose first time, 50% dose second time, discontinue third time.

5.7.2.3 Treatment discontinuation criteria for IMP

For nivolumab, treatment will be permanently discontinued for the following reasons (in CTCAE grading):

- Any grade 4 drug-related AE.
- Any grade 2 drug-related uveitis, eye pain, or blurred vision that does not respond to topical therapy and does not improve to grade 1 severity within the re-treatment period or requires systemic treatment.
- Any grade 3 non-skin, drug-related AE lasting >7 days, with the following exceptions for laboratory abnormalities, drug-related uveitis, pneumonitis, bronchospasm, hypersensitivity reactions, infusion reactions, and endocrinopathies:
 - Grade 3 drug-related uveitis, pneumonitis, bronchospasm, hypersensitivity reaction, or infusion reaction of any duration (requires discontinuation).
 - Grade 3 drug-related endocrinopathies that are adequately controlled with only physiologic hormone replacement (do not require discontinuation).
 - Grade 3 drug-related laboratory abnormalities (do not require treatment discontinuation) except grade 3 drug-related thrombocytopenia >7 days or associated with bleeding (requires discontinuation).
- Any drug-related liver function test abnormality that meets the following criteria (requires discontinuation):
 - AST or ALT >5xULN.
 - Total bilirubin >3xULN.
- Any grade 4 drug-related AE or laboratory abnormality, except for one of the following events (does not require discontinuation):
 - Grade 4 neutropenia ≤7 days.
 - Grade 4 lymphopenia or leukopenia.
 - Isolated grade 4 amylase or lipase abnormalities that are not associated with symptoms or clinical manifestations of pancreatitis. Study Conduct Group (*c.f.*, [Paragraph 11.3](#)) should be consulted for grade 4 amylase or lipase abnormalities.
 - Isolated grade 4 electrolyte imbalances/abnormalities that are not associated with clinical sequelae and are corrected with supplementation/appropriate management within 72 hours of their onset.
 - Grade 4 drug-related endocrinopathy adverse events, such as adrenal insufficiency, ACTH deficiency, hyper- or hypothyroidism, or glucose intolerance, which resolve or are adequately controlled with physiologic hormone replacement (corticosteroids, thyroid hormones) or glucose-controlling agents, respectively, may not require discontinuation after discussion with and approval from Study Conduct Group.
- Any event that leads to delay in dosing lasting >6 weeks from start of the previous therapy cycle requires discontinuation, with the following exceptions:
 - Dosing delays to allow for prolonged steroid tapers to manage drug-related adverse events (allowed).
 - Dosing delays lasting >6 weeks from the previous dose that occur for non-drug-related reasons (may be allowed if approved by Study Conduct Group).
 - Prior to re-initiating treatment in a subject with a dosing delay lasting >6 weeks, Study Conduct Group must be consulted. Tumor assessments should continue as per protocol even if dosing is delayed. Periodic study visits to assess safety and laboratory studies should also continue every 6 weeks or more frequently if clinically indicated during such dosing delays.
- Any AE, laboratory abnormality, or intercurrent illness which, in the judgment of Clinical Investigator, presents a substantial clinical risk to the subject with continued nivolumab dosing.

For detailed information, please refer to the IB for nivolumab.

For FLOX, treatment will be permanently discontinued for the following reasons (in CTCAE grading):

- Grade 4 diarrhea (life-threatening consequences, urgent intervention indicated).
- Grade 3 sensory neuropathy (sensory alteration or paresthesia, severe symptoms, limiting self-care ADL).

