8.1 Definitions

An AE is defined as any new untoward medical occurrence or worsening of a preexisting medical condition in a subject administered a study drug and which does not necessarily have a causal relationship with this treatment. An AE can therefore be any unfavorable and unintended sign (including an abnormal laboratory finding), symptom, or disease temporally associated with the use of a medicinal (investigational) product, whether or not cautiously related to the medicinal (investigational) product.

The causal relationship to a study drug is determined by a physician and can be one of the following:

- Related: There is a reasonable causal relationship between study drug administration and the AE.
- Not related: There is not a reasonable causal relationship between study drug administration and the AE.

The term “reasonable causal relationship” means there is evidence to suggest a causal relationship. AE can be spontaneously reported or elicited during open-ended questioning, examination, or evaluation of a subject.

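### Protocol 5.7.2.3 permanently stops nivolumab for every grade 4 drug-related AE and, in the same list, exempts some grade 4 events; the unqualified stop should go

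*Protocol*

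**What the plan says.** Each nivolumab bullet in Protocol 5.7.2.3 is by itself a reason for permanent discontinuation. Two of them cover grade 4 events:

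- The first bullet reads "Any grade 4 drug-related AE". No exception is attached.
- A later bullet reads "Any grade 4 drug-related AE or laboratory abnormality, except for one of the following events (does not require discontinuation" and then names five kinds of event. They include "Grade 4 neutropenia ≤7 days", "Grade 4 lymphopenia or leukopenia" and "Grade 4 drug-related endocrinopathy adverse events, such as adrenal insufficiency, ACTH deficiency, hyper- or hypothyroidism, or glucose intolerance". If resolved or adequately controlled, the endocrinopathies "may not require discontinuation after discussion with and approval from Study Conduct Group". The remaining two are isolated amylase or lipase abnormalities and isolated electrolyte abnormalities.

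Protocol 5.7.2.2 points the same way as the exceptions: "Subjects with drug-related endocrinopathies adequately controlled with only physiologic hormone replacement may resume treatment". It sets no grade limit.

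Protocol 8.1 defines an AE to include "any unfavorable and unintended sign (including an abnormal laboratory finding", whereas 5.7.2.3 mostly writes AE and laboratory abnormality as separate items.

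The nivolumab delay list in 5.7.2.1 has four bullets: non-skin drug-related AEs of grade 2 or higher, leaving out fatigue and laboratory abnormalities; skin AEs at grade 3; laboratory abnormalities at grade 3; and anything the investigator judges to warrant a delay.

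**The concern.** The two grade 4 stop rules cannot both be followed. Take a patient with grade 4 adrenal insufficiency controlled on replacement. Under the first bullet nivolumab ends for good; under the later bullet it may continue once the Study Conduct Group agrees. Nothing in the Protocol says which bullet prevails, so centers could handle the same event differently.

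The choice also affects the delay list. If the exceptions prevail, some grade 4 laboratory events are not a stop. The delay list then requires a hold for the milder grade 3 value but names none for the worse one. Separately, severe fatigue of short duration has no required hold under either reading.

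What is at stake is consistent and safe dosing in the experimental arm.

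**Working it through.** No arithmetic in the plan bears on this, so the check traces each exempt event through the stop list (5.7.2.3) and the nivolumab delay list (5.7.2.1).

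| Exempt grade 4 kind | Conflicts with first stop bullet? | Mandatory nivolumab hold if exceptions govern? | Other limit in 5.7.2.3 |
|---|---|---|---|
| Neutropenia | Only through 8.1 | No | 7 days or less |
| Lymphopenia or leukopenia | Only through 8.1 | No | None |
| Isolated amylase/lipase | Only through 8.1 | No | Study Conduct Group should be consulted |
| Isolated electrolytes | Only through 8.1 | No | Corrected within 72 hours |
| Resolved or controlled endocrinopathy | Yes; the section calls it an adverse event | Yes, by the first delay bullet | Study Conduct Group approval |

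**Count.** Of 5 exempt kinds, 1 conflicts on the section's own wording and 5 − 1 = 4 conflict only through 8.1. The same 4 have no mandatory hold if the exceptions govern. Electrolytes carry a 72-hour limit and amylase/lipase carries a consultation, so 4 − 2 = 2 matter in practice: neutropenia of 7 days or less, and lymphopenia or leukopenia.

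**Three ways to resolve the conflict.**

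1. The first bullet governs and AE includes laboratory findings. All five kinds stop, the exception list has no effect, and there is no laboratory hold gap.
2. The first bullet governs but AE excludes laboratory findings. The endocrinopathy exception has no effect, and the hold gap for the four laboratory kinds remains.
3. The exceptions govern. The list works as evidently intended, and the hold gap for the four laboratory kinds remains.

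**Why there is a hold gap.** The first delay bullet leaves out laboratory values, the second covers skin only, the third names grade 3 only, and the fourth is discretionary. Using the grade limits printed in 5.7.2.1 (grade 3 neutrophils from 0.5 to below 1.0 ×10⁹/L, grade 4 below 0.5):

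- Neutrophils of 0.7: nivolumab must be held.
- Neutrophils of 0.4 for 7 days or less: neither a stop nor a mandatory nivolumab hold under readings 2 and 3, and a permanent stop under reading 1. If FLOX is the drug due, a hold is mandatory, because the FLOX list names grade 4 myelosuppression.

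**Fatigue.** The first delay bullet leaves out fatigue at every grade. The grade 3 non-skin stop in 5.7.2.3 applies only beyond 7 days. Grade 3 fatigue of 7 days or less therefore has no mandatory hold, although 5.7.2.2 accepts fatigue no worse than grade 2 at restart.

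**Does deleting the first stop bullet lose protection?** No. The later bullet covers all grade 4 drug-related AEs and laboratory abnormalities apart from the five exempt kinds, so every non-exempt grade 4 event still stops nivolumab.

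**The case against.** The strongest reply is that the first bullet is a leftover line and the resolution is plain. The later bullet repeats it, widens it and attaches detailed exceptions, one with its own approval step. Those exceptions would serve little purpose if the first bullet prevailed. Endocrinopathy goes to a central group, which limits variation between centers, and a site that wrongly follows the first bullet errs toward caution on toxicity. This stands as to intent. It does not remove the defect, because each bullet suffices alone and a site applying the first one never reaches the approval step.

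On the delay list, 5.7.2.1 opens by applying its criteria to all drug-related AEs, and 5.7.2.2 by default requires recovery to grade 1 or baseline. Both suggest that worse events were meant to be held. But the opening sentence sets the scope and names no hold, and restart criteria apply only after a dose has been held.

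Safeguards also exist: investigator judgment, the general permission in 5.7.1 to delay doses, laboratory tests within 3 days before each dose (7.4), and the external committee's count of grade 3–5 events (10.4.2). They permit or prompt a hold without requiring one. The windows are narrow too: the event must be present when a nivolumab dose falls due. Finally, the algorithm groups named for Appendix 5 include endocrinopathy but neither blood counts nor fatigue; Appendix 5 and the Investigator's Brochure are not reproduced. These points keep the delay-list gaps minor and the confidence in them limited.

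**Conclusion.** The contradiction in 5.7.2.3 is real and wrong as written. It is certain for resolved or controlled grade 4 endocrinopathy, and for the four laboratory kinds it depends on applying 8.1. The delay-list gaps are secondary. They hold on the literal text only and are subject to Appendix 5 and the Investigator's Brochure; the laboratory gap also requires that the first stop bullet does not reach laboratory values. In both gaps a hold is allowed by investigator judgment but not required.

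A reader might infer that all five exemptions conflict outright, that grade 4 toxicity in general escapes a stop or hold, or that affected patients would in fact be dosed. The documents do not support this. Four conflicts run only through 8.1, non-exempt grade 4 events are still stopped, endocrinopathy is held by the first delay bullet, and discretionary holds remain open. Nor does anything here touch the PFS definition, power or alpha.

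Severity is minor, and the category is internal inconsistency. Without event rates, the number of patients or doses affected cannot be estimated.

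**What to change.** 1. **5.7.2.3, first bullet:** delete it. The later grade 4 bullet, with its exceptions, then governs.
2. **5.7.2.1, first nivolumab bullet:** keep the grade 2 threshold but reorder and narrow the exceptions, for example: *exceptions are laboratory abnormalities (see third bullet) and grade 2 fatigue*. Naming laboratory values first prevents grade 2 from being read as qualifying both.
3. **5.7.2.1, third nivolumab bullet:** extend it from grade 3 to *grade 3 or higher, where 5.7.2.3 does not require discontinuation*.
4. **5.7.2.3, six-week limit:** add that a delay due solely to lymphopenia or leukopenia does not by itself require discontinuation if the Study Conduct Group approves. Without this, holding a persistent grade 4 lymphopenia until grade 1 or baseline could pass 6 weeks from the previous cycle start (6 − 2 = 4 weeks of delay on a 2-week cycle). That would turn an event exempt for any duration into a stop.

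The cost is one amendment with four short text changes. The downside is a few more nivolumab holds, number unknown. Before finalizing items 2 and 3, the sponsor should check them against Appendix 5 and the Investigator's Brochure.

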8.4 Laboratory test abnormalities

The following laboratory test abnormalities will be captured on the non-serious AE CRF page or SAE report form as appropriate:

- Any laboratory test result that is clinically significant or meets the definition of SAE.
- Any laboratory test result abnormality that requires the subject to have study drug discontinued or unintendedly interrupted.
- Any laboratory test result abnormality that requires the subject to receive specific corrective therapy.

It is expected that wherever possible, the clinical rather than laboratory term would be used by the reporting investigator (e.g., anemia *versus* low hemoglobin value).

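### Protocol 5.7.2.3: the unconditional grade 4 stop bullet for nivolumab contradicts the later exemption for controlled endocrinopathies (minor, but wrong as written)

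*Protocol*

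**What the plan says.** The nivolumab list in Protocol 5.7.2.3 is mandatory: each of its seven top-level bullets is a reason for permanent discontinuation. Two of them deal with grade 4 drug-related events in general.

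- The first bullet reads "Any grade 4 drug-related AE" and ends there. It has no exceptions and no cross-reference.
- The fifth bullet reads "Any grade 4 drug-related AE or laboratory abnormality, except for one of the following events (does not require discontinuation" and then lists five exempt categories: neutropenia of up to 7 days; lymphopenia or leukopenia; isolated amylase or lipase abnormalities without pancreatitis; isolated electrolyte abnormalities without sequelae that are corrected within 72 hours; and endocrinopathies.

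The endocrinopathy exemption covers "Grade 4 drug-related endocrinopathy adverse events, such as adrenal insufficiency, ACTH deficiency, hyper- or hypothyroidism, or glucose intolerance" where these resolve or are adequately controlled by hormone replacement or glucose-controlling agents. Such events "may not require discontinuation after discussion with and approval from Study Conduct Group".

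Protocol 5.7.2.2, on resuming after a delay, adds: "Subjects with drug-related endocrinopathies adequately controlled with only physiologic hormone replacement may resume treatment". It states no grade limit.

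**The concern.** A stop rule for grade 4 toxicity should give one answer per patient. Take a patient with grade 4 drug-related adrenal insufficiency, controlled on physiologic replacement, whose continuation the Study Conduct Group approves. The first bullet requires a permanent stop. The fifth allows treatment to go on.

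A site that follows the first bullet withdraws the investigational drug from a patient whom the protocol evidently meant to keep on it. A site that follows the fifth has central approval but has also broken a stop rule. Significant protocol deviations must be recorded and reported (Protocol 11.2, SAP 3.2), so the patient's deviation status depends on which bullet is read as governing.

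**Working it through.** No arithmetic formula applies and the plan gives no figure to reproduce. The check is a comparison of the provisions.

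**Step 1. Where the two bullets agree.** For a grade 4 drug-related adverse event outside the five exempt categories, both bullets require a permanent stop. Any conflict is confined to the exempt categories.

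**Step 2. Endocrinopathy.** The fifth bullet itself describes these as adverse events ("Grade 4 drug-related endocrinopathy adverse events, such as adrenal insufficiency, ACTH deficiency, hyper- or hypothyroidism, or glucose intolerance"). They are grade 4, drug-related and adverse events, so they meet every term of the first bullet. They cannot be set aside as laboratory values. The first bullet says stop; the fifth says a stop may not be required, given approval. This conflict is direct.

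**Step 3. The four laboratory categories.** Here the first bullet applies only if the abnormality counts as an adverse event. The protocol's wording is mixed:

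| Provision | Bearing on adverse event status |
|---|---|
| 8.1: "An AE can therefore be any unfavorable and unintended sign (including an abnormal laboratory finding), symptom, or disease" | A laboratory finding can be an adverse event |
| 5.7.2.3, third bullet, and 5.7.2.1 | Laboratory abnormalities are carved out of an adverse event trigger, which suggests they would otherwise fall within it |
| 5.7.2.3, fifth and last bullets | Adverse events and laboratory abnormalities are named as separate items |
| 8.1.1 | When a value comes with symptoms, the symptom is reported as the adverse event and the value is supporting information |
| 8.4, besides results of clinical significance: "Any laboratory test result abnormality that requires the subject to receive specific corrective therapy" | Such results go on the adverse event or serious adverse event form; this governs recording and sets no stop trigger |

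The electrolyte category comes nearest to adverse event status, because its exemption presupposes correction and 8.4 captures abnormalities needing corrective therapy. That is still a rule about forms. All four laboratory categories remain conditional.

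**Step 4. Count.** Exempt categories: 5. Direct conflict: 1 (endocrinopathy). Conditional: 4 (neutropenia, lymphopenia or leukopenia, amylase or lipase, electrolytes). 1 + 4 = 5.

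**Step 5. Which bullet was meant.** Two things point to the fifth. It restates the first bullet's trigger in full and then qualifies it; if the first bullet governed, the endocrinopathy exemption would have no function, and the laboratory exemptions would have none either wherever the value is an adverse event. And 5.7.2.2 lets hormone-controlled endocrinopathies resume, which fits the fifth bullet. The second point shows intent only: 5.7.2.2 governs resumption after a delay, so a patient already stopped permanently never reaches it. It is also narrower than the exemption, since it does not mention glucose-controlling agents.

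**Step 6. Reach into the analysis.** Protocol 10.4 and SAP 5.2 do not condition the progression-free survival comparison, or any other efficacy analysis, on nivolumab continuation or deviation status. A per-protocol population is defined (Protocol 10.3, SAP 3.3), but no analysis is assigned to it.

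**The case against.** The strongest reply is that the first bullet is a leftover duplicate, that any sensible reader lets the specific rule override the general one, and that the only direct conflict is already gated. No site can continue nivolumab after a grade 4 endocrinopathy without Study Conduct Group approval, so neither reading produces an unsupervised continuation.

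Most of this stands. It is why the point is minor. It does not remove the contradiction: the list is mandatory, and its third bullet (grade 3 events) shows that the authors attach exceptions directly to the rule they qualify. The first bullet has none, so a literal reader could take it as absolute.

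Two stronger readings are tempting and are not supported.

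- A reader might infer that the first bullet cancels all five exemptions. That requires every laboratory abnormality to be an adverse event. Section 8.1 says only that one can be, and the fifth bullet names the two separately.
- A reader might infer that the nivolumab delay trigger in 5.7.2.1 must also change, from grade 3 to grade 3 or higher laboratory abnormalities, because an exempt grade 4 laboratory event now delays dosing only at the investigator's judgment. That gap exists whether or not the first bullet is removed. Closing it this way would be a change of dosing policy: grade 4 lymphopenia or leukopenia is exempt without a time limit, but a mandatory delay until the 5.7.2.2 recovery criteria are met would run into the 6-week limit in 5.7.2.3, so the exemption would become time-limited.

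**Conclusion.** The point holds as a minor drafting error. The first bullet and the endocrinopathy exemption in 5.7.2.3 cannot both be followed when a controlled grade 4 drug-related endocrinopathy has been approved for continuation. The conflict is direct for 1 of 5 exempt categories and conditional on adverse event classification for the other 4.

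The consequence is limited to whether individual experimental-arm patients stay on nivolumab and whether staying on it is a deviation. A reader might infer a threat to the trial's results; the documents do not support that, since no planned efficacy analysis changes. The number of patients affected cannot be computed, because no rates of these events are given.

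One assumption matters: that nothing outside the available text settles the order. The nivolumab Investigator's Brochure, the external document behind Appendix 5, and section 11.3 on the Study Conduct Group were not available to this review.

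**What to change.** Delete the first nivolumab bullet in 5.7.2.3. The fifth bullet already contains the same trigger, so no stop criterion is lost. Alternatively, keep the first bullet and add that it is subject to the exceptions listed below. Either way one grade 4 stop rule remains.

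The cost is one deleted or amended line, submitted as a protocol amendment under 11.4. Nothing changes in the SAP, the sample size or data collection. The delay trigger in 5.7.2.1 is not part of this fix; if the sponsor wishes to revisit it, that should be a separate dosing decision.
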